6.3. Success criteria

Progression to a definitive trial will be considered if the following a priori success criteria are met:

- Recruitment rate: ≥ 2 participants per month (30 participants recruited in 18 months)
- Safety - The following traffic light-style system is proposed:
 - Red: >10 adverse events related to the intervention – do not proceed.
 - Amber: 5-10 adverse events related to the intervention – review and revise protocol.
 - Green: <5 adverse events related to the intervention – proceed.
- Acceptability: average comfort score $> 3/5$ Likert scale (1= very uncomfortable to 5= very comfortable).
- Completeness of data: $>80\%$ of planned measurements recorded.
- Identification of an appropriate outcome measure.

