7.3. Sample size

A minimum of 24 participants (12 per arm) will be recruited. 12 has been recommended as a minimum number of participants per arm to be recruited for a clinical trial where there is no prior information to guide sample size (60). This figure is suggested to represent the lower threshold required to estimate the standard deviation of measures with adequate precision (60). Adjusting for a predicted 20% attrition rate, the target sample size is 30.

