7.7. Consent and withdrawal

Participants will only be enrolled in the study if they have capacity to understand the participant information sheet and give informed consent. An aphasia-friendly participant information sheet will be made available. All written material given to patients will have prior approval from a local NHS Research Ethics Committee (REC) and will comply with GCP, local regulatory requirements and legal requirements. Where participants have the capacity to understand the study and are willing to participate but cannot write due to motor impairment, a family member will be asked to sign on the patient's behalf. All research team members involved in recruitment have received training in communication with people that have communication difficulties (e.g. aphasia). Participants will be informed that their participation is voluntary and that they may withdraw from the study at any time without giving a reason and without it affecting their clinical care or legal rights. Any data provided to that point will be used unless the patient requests otherwise. If the patient requests to have their data withdrawn, all data relating to that participant up until anonymisation of the final dataset will be destroyed.

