9.5. Preparation, storage and analysis of blood samples

Venous blood samples will be taken at t_5 (6-8 days post-stroke). Baseline blood samples will be collected from control and intervention group participants in a resting state. Post-exercise blood samples will be taken from the intervention group participants during the recovery (passive cycling) phase following aerobic exercise.

Blood samples will then be centrifuged and aliquoted at RHH. Processed samples will then either be stored in a designated -80°C freezer at RHH or put on ice (for up to 5 hours) and transferred to the AWRC and stored at stored at -80°C. mBDNF will be measured using an enzyme-linked immunosorbent assay (116). Platelet count will be measured using an automated haematology analyser. Blood plasma volume will be measured using the Dill and Costill method (117). Blood samples will be stored for 10 years to allow time to source additional funding and obtain ethical approval for further exploratory analyses that may improve mechanistic knowledge. 10 years after the trial end date samples will be destroyed in accordance with local laboratory procedures. Researchers are trained in venepuncture.

10. COVID-19 contingency plan

Currently, non-essential face-to-face research is suspended due to the COVID-19 pandemic. A restart date has not yet been announced, however it is unlikely that the proposed study will be able to take place before the end of 2020 due to the combination of winter pressures and a second wave of COVID-19-related hospital cases. If the proposed study is approved and is able to commence in the early months of 2021, we anticipate that patient follow-up appointments will be conducted virtually (via video call or telephone) for a transitional period of an unknown duration. Thus, the research activities that are planned to be conducted at follow-up appointments may be adapted or omitted. Table 5 outlines our contingency planning for research-related activities. In line with STH procedures, participants will be given an information leaflet providing technical support with regards to video call and telephone consultations. All face-to-face research activities will be conducted in accordance with STH risk management policy.

Table 5. COVID-19 contingency plan

Activity/measure	Plan A (no face-to-face research restrictions)	Plan B (COVID-19 restrictions)

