Recruitment rate	Number of participants recruited per month of the recruitment period.
Exclusion rate	Number of ineligible patients divided by the total number of patients admitted to the RHH stroke service during the recruitment period.
Consent rate	Percentage of eligible patients who consent to participate.
Dropout rate	Percentage of individuals that discontinue participation after the study has commenced. Voluntary reasons for dropout will be recorded. Early discharge from hospital will not count as a dropout.
Participant fidelity	Completion of key exercise components in accordance with the exercise protocol including: percentage of planned exercise session duration completed, percentage of target exercise intensity per session attained, and percentage of total planned exercise sessions completed.
Completeness of data	Percentage of planned measurements completed and recorded.
Safety	Number of SAE and AEs related to the intervention.
Acceptability of intervention (participant interview)	Comfort and ease of using cycling apparatus.
Acceptability of study procedures (healthcare professional interview)	
 • Attitudes towards the intervention • Burden on staff and participants • Perceived effectiveness of the intervention

12. Intervention

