
The day after completing the first exercise bout, participants will undertake a single aerobic exercise session per day for 4 days (5 exercise sessions in total). If patients are discharged earlier, study participation will terminate on the day of discharge. The workload that elicited an RPE of 13 at the start of the conditioning phase in the first aerobic exercise session will be used to guide the initial workload for the conditioning phase in subsequent sessions.

Number of repetitions (rpm multiplied by minutes) completed during the warm-up,

conditioning phase and cool-down will be included within therapy dose calculations. Verbal communication provided by the operator will be standardised (detailed in Table 6, Appendix).

Through consultations with stroke survivors and healthcare practitioners we acknowledge the need for a flexible exercise protocol. It was expressed to us that patients' level of fatigue and physical function may fluctuate throughout the duration of hospital stay depending on various intrinsic and extrinsic factors. Thus, the workload used for each exercise session will be a collaborative choice made between the researcher and the participant.

[figure not shown]

Figure 5. Schematic diagram of 5-day exercise protocol.

Note: Blue = passive cycling (no exertion) = 5 minutes; brown = warm up/cool down; pink = active cycling (moderate intensity). Active cycling duration = 5 minutes per bout. Passive recovery intervals = 1 minute (blue).

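### The completeness criterion pools all planned measurements over visits and arms, so it does not protect the 3-month outcomes

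*Protocol*

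**What the plan says.** Protocol section 6.3 lists the a priori criteria for considering a definitive trial. The one on data is more than 80% "of planned measurements recorded". Table 6 (section 11) defines the measure as "Percentage of planned measurements completed and recorded". Neither place gives a threshold by outcome, visit or arm.

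Section 7.3 sets the size of the trial: "A minimum of 24 participants (12 per arm) will be recruited", and then "Adjusting for a predicted 20% attrition rate, the target sample size is 30".

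Three further statements bear on what enters the percentage:

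- Withdrawal (section 7.7): "Any data provided to that point will be used unless the patient requests otherwise".
- Early discharge. Table 6 says "Early discharge from hospital will not count as a dropout", while section 12.3.3 says "If patients are discharged earlier, study participation will terminate on the day of discharge".
- COVID-19 (section 10): "the research activities that are planned to be conducted at follow-up appointments may be adapted or omitted". Table 5 then omits thigh ultrasound, the SPPB, 10-m walk, handgrip, the acute fatigue rating and the MoCA at 3 months under Plan B.

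Table 3 is the only list of what is planned. After baseline it schedules the MoCA, FSS, GAD-7/PHQ-9 and EQ-5D at 3 months only. It also plans heart rate, blood pressure, perceived exertion and oxygen saturation at each of five exercise sessions, in the intervention arm alone.

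**The concern.** Aim 4 is to choose a primary outcome for the definitive trial from the group difference and the variability of each candidate measure. The trial summary names physical function, quality of life, cognition, mood and fatigue among the candidates. Several of these have no post-baseline value other than the one at 3 months, so if that visit fails they give no between-group estimate.

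A pooled percentage gives that visit only its share of the item count. Inpatient items are more numerous and are collected while the participant is on the ward. Per-session exercise readings add 20 items per intervention participant (4 readings × 5 sessions). The criterion can then read as met when follow-up has largely failed, and no other criterion in 6.3 puts a number on follow-up.

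**Working it through.** **The plan's own figure.** 24 / (1 − 0.20) = 30, as section 7.3 states.

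**Counting planned items.** Counts come from Table 3, for 15 participants per arm. The table is broken in the text at hand and the protocol does not define a planned measurement, so six conventions were used. Assumptions: Barthel Index at four visits; mRS at three visits as in Table 3 (Table 5 adds 2 weeks); fatigue ratings at four exercise sessions; interviews in 8 of 15 per arm.

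Let s be the share of items due at 3 months and m the fraction of earlier items missing. The largest fraction of 3-month items that can be missing at the 80% boundary is

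(0.20 − m(1 − s)) / s, capped at 1.

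| What is counted | 3-month / all items | s | m = 0 | m = 5% | m = 10% |
|---|---|---|---|---|---|
| Outcomes, by instrument | 496 / 1592 | 31.2% | 64% | 53% | 42% |
| + exercise-session monitoring | 496 / 2027 | 24.5% | 82% | 66% | 51% |
| + adverse-event checks | 526 / 2297 | 22.9% | 87% | 71% | 54% |
| + procedural items | 526 / 2567 | 20.5% | 98% | 78% | 59% |
| Table rows, outcomes and exercise | 406 / 1772 | 22.9% | 87% | 70% | 54% |
| Table rows, everything | 436 / 2312 | 18.9% | 100% | 85% | 63% |

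Worked example, first row: m = 0 gives 0.20 / 0.312 = 0.64; m = 10% gives (0.20 − 0.10 × 0.688) / 0.312 = 0.42.

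**Plan B as an illustration.** In the first row, the measures that Plan B omits make up 6 of the 3-month items per participant (thigh ultrasound 1, physical function 3, acute fatigue 1, MoCA 1). If all were lost and counted as missing, with everything else complete, the pooled figure would be 1 − (6 × 30) / 1592 = 88.7%. The criterion would be met with no MoCA value after baseline.

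**Pooled rule at the planned 20% attrition.**

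- All dropouts miss only the 3-month visit: 1 − 0.20s = 93.8% to 96.2%.
- All leave straight after baseline: 1 − 0.20 × (share of items after baseline) = 84.1% to 85.7%.
- It falls to 80.0% only if the 20% contribute nothing at all.

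**The same threshold on one 3-month outcome.** 24 / 30 = 80.0%, which is not above 80%. The strict inequality needs 25 / 30 = 83.3%.

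**How demanding a per-outcome rule would be**, taking retention as independent binomial with true attrition of 20%:

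- at least 24 of 30 overall: 61%;
- at least 12 of 15 in both arms: 0.648² = 42%.

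**The case against.** A reader might infer that the criterion contradicts the protocol's own 20% attrition. The documents do not support that. Section 7.7 keeps what participants gave before withdrawing, so the pooled figure stays at about 84–96% and passes. The 24/30 shortfall appears only if the threshold is applied to a 3-month outcome, which neither 6.3 nor Table 6 does.

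A reader might also infer that the rule can generally be met with a handful of participants at follow-up. A count by table row with exercise monitoring does give about 4 of 30 (12.7% × 30 = 3.8), but only if every earlier item is complete. With 10% of earlier items missing and outcomes alone counted, about 18 of 30 are needed (58% × 30 = 17.4). Early discharge makes some loss of inpatient items foreseeable.

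There are other fair points. Objective 1c concerns completeness of the whole planned collection, and no section fixes 3 months as the definitive endpoint. NIHSS, mRS, Barthel and the physical function tests are also scheduled the day after the intervention. Dropout is reported as a feasibility outcome, 6.3 also asks that an appropriate outcome measure be identified, and progression is only to be considered, so a collapse of follow-up would be seen. A breakdown by visit could also be given in an analysis plan.

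These points limit the consequence but do not remove the defect. Neither dropout nor the identification of an outcome carries a number in 6.3. The threshold is a decision rule that the protocol itself fixes, and as fixed it is insensitive to the 3-month visit.

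**Conclusion.** The point stands in limited form. As written, the criterion can be met with roughly 40% to all of the 3-month data missing, depending on what counts as a planned measurement and how complete the earlier items are. More than half can be missing under every convention when no more than 5% of earlier items are lost. At 10%, the outcomes-only count allows 42%. The result rests on approximate counts from a broken table and on the assumptions listed with them, but its direction is the same under all six counts.

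There is no conflict with the planned attrition. The strict inequality matters only if the threshold is moved to individual 3-month outcomes. The denominator is also left open for early discharge and for Plan B omissions. This is a cheap improvement: the other feasibility results would still be reported, but this criterion by itself says little about whether the definitive trial could measure its primary outcome.

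**What to change.** Change the wording in section 6.3 and Table 6:

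1. Report completeness by outcome and visit, with all randomised participants as denominator.
2. Require that any outcome put forward as the definitive trial's primary has at least 80% recorded (≥, not >) at its intended time point, for example 24 of 30 at 3 months.
3. Report per-arm numbers against the 12 per arm in 7.3, but do not make them a separate pass/fail rule. At the planned attrition, both arms would reach 12 only about 42% of the time.
4. State how measures omitted under Plan B, and those due after an early discharge, are counted.
5. Keep the pooled percentage as description only.

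No extra data are needed. The cost is a criterion that is somewhat harder to meet: about a 61% chance per outcome if true attrition is exactly 20%, before any item-level missing data.

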6.4. Study flow chart

[figure not shown]

Figure 3. Study flow chart

7.1. Patient throughput and planned recruitment

According to NHS England figures, RHH HASU will receive approximately n=1335 stroke patient admissions in 2019/20 (58). 85% of these patients will have had an ischaemic stroke (6), thus, ~1135 ischaemic stroke survivors will potentially be eligible for our study per year (n=1700 in 18 months). A systematic review of recruitment rates in stroke rehabilitation trials suggests that 1.5 to 2 participants per month is a realistic target for a single site (59); hence, our recruitment target of 30 patients over 18 months.

7.2. Recruitment strategy

The Study Doctor will identify eligible patients located on the HASU, the ASU and the neurology day care unit. Eligibility will be determined in accordance with the inclusion and exclusion criteria. Daily ward rounds will be the primary means of identifying eligible patients. Once identified, the Study Doctor and an Investigator will greet eligible patients and inform them about the study. Patients will be informed about the potential risks, benefits and burden of participating, and will be made aware of the randomised group allocation procedure. Patients will be provided with a participant information sheet and will be politely asked to contemplate the information and make a decision within 48 hours of the initial discussion. This is due to the time-sensitive nature of the research. An aphasia-friendly version of the participant information sheet will be made available. A notepad and pen will be provided for patients with dysarthria (speech disorder). Where possible, family members and other supporting individuals will be informed about the study. At a later time point, an Investigator and the Study Doctor will revisit the patient at a mutually convenient time to answer any questions the patient, family member or supporting individual may have about the study. Patients will then be asked if they would like to participate. If they are willing to participate, informed consent will be taken. If the patient is undecided, the Investigator and the Study Doctor will return at a later time point (<48hrs of initial discussion) and repeat the process.

7.3. Sample size

A minimum of 24 participants (12 per arm) will be recruited. 12 has been recommended as a minimum number of participants per arm to be recruited for a clinical trial where there is no prior information to guide sample size (60). This figure is suggested to represent the lower threshold required to estimate the standard deviation of measures with adequate precision (60). Adjusting for a predicted 20% attrition rate, the target sample size is 30.

7.4. Inclusion criteria

- Adult (age >18 years) patients diagnosed with acute ischaemic stroke 1-7 days previously.
- Medically stable, assessed by a stroke physician.
- Sufficient English language comprehension and cognitive ability to understand the study protocol, follow instructions, complete questionnaires and give informed consent.
- Ability to mobilise lower body limbs in a cyclical manner (at least one leg).

7.5. Exclusion criteria

The following criteria are adapted from (45,61,62).

- Haemorrhagic stroke.
- <1 day or >7 days after onset of stroke symptoms.
- Clinically unstable, assessed by stroke physician.
- Disability preventing unipedal cycling.
- New York Heart Failure Classification stage III/IV.
- Terminal illness (life expectancy <6 months).
- Resting blood pressure >180/110 mmHg.
- Uncontrolled arrhythmia causing symptoms or haemodynamic compromise.
- Unstable angina.
- Uncontrolled diabetes mellitus.
- Acute deep vein thrombosis, pulmonary embolism or pulmonary infection.
- Already participating in a clinical research trial.
- Pain during mobilisation of lower limbs.
- Lower-limb spasticity or contracture which impairs ability to cycle.

7.6. Patient screening

The Study Doctor will review patients' clinical data to determine eligibility in accordance with the inclusion and exclusion criteria. Patients will be screened for absolute and relative contraindications to aerobic exercise prior to participation (Table 1, section 8.1). Absolute contraindications will preclude individuals from undertaking aerobic exercise. The Study Doctor will use clinical judgment to determine if individuals with relative contraindications to aerobic exercise can participate. Established exercise termination criteria (Table 2, section 8.2) will be used to minimise risk of harm during aerobic exercise.

The following routine medical examinations and clinical information will be used to determine eligibility and stratification:

- Time and date of stroke onset.
- Stroke treatments initiated.
- Stroke severity.
- Medication use.
- Electrocardiography results.
- Blood test results.
- Neuroimaging results.
- Carotid ultrasound imaging results.
- Comorbidities.

7.7. Consent and withdrawal

Participants will only be enrolled in the study if they have capacity to understand the participant information sheet and give informed consent. An aphasia-friendly participant information sheet will be made available. All written material given to patients will have prior approval from a local NHS Research Ethics Committee (REC) and will comply with GCP, local regulatory requirements and legal requirements. Where participants have the capacity to understand the study and are willing to participate but cannot write due to motor impairment, a family member will be asked to sign on the patient's behalf. All research team members involved in recruitment have received training in communication with people that have communication difficulties (e.g. aphasia). Participants will be informed that their participation is voluntary and that they may withdraw from the study at any time without giving a reason and without it affecting their clinical care or legal rights. Any data provided to that point will be used unless the patient requests otherwise. If the patient requests to have their data withdrawn, all data relating to that participant up until anonymisation of the final dataset will be destroyed.

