12.5. Recording and reporting of serious adverse events

All SAEs occurring from the time of start of the intervention until 3 months post cessation of trial intervention will be recorded on a STH-approved form and faxed/mailed to the Sponsor within 24 hours of the research staff becoming aware of the event. Once all resulting queries have been resolved, the Sponsor will request that the original form should also be posted to the Sponsor and a copy to be retained on site.

For each SAEs the following information will be collected:

- Full details in medical terms and case description.
- Event duration (start and end dates, if applicable).

- Action taken.
- Outcome.
- Seriousness criteria.
- Causality (i.e. relatedness to intervention), in the opinion of the Investigator.
- Whether the event would be considered anticipated.

Any change of condition or other follow-up information should be emailed/faxed to the Sponsor as soon as it is available or at least within 24 hours of the information becoming available. Events will be followed up until the event has resolved or a final outcome has been reached.

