Where possible, all participant data will be coded using unique reference numbers (pseudo-anonymised). All hard copy data will be stored securely in the site file located in a locked office. The location of the site file will be specified to the Sponsor and regulatory bodies. The site file will be accessible to authorised individuals upon request. Scanned copies of hard copy data will be saved as encrypted PDFs and stored in the university SHU Research Store. Qualitative data will be recorded on encrypted Dictaphones and downloaded in either MP3. or WAV format as soon as possible after data collection. Audio recordings of interviews will be destroyed after they have been transcribed. Digital data will be transferred between devices using <https://zendto.shu.ac.uk>, which is an encrypted platform that enables users to upload and download data. If the internet is inaccessible, an encrypted external hard drive will be used to transfer data instead. Data will be transferred as soon as possible from the external hard drive to the relevant device and will be deleted from the hard drive after being transferred. Relevant data will be input into encrypted Microsoft Excel spreadsheets and saved in XLS format. Data will be analysed in SPSS version 24.0 according to established statistical principles. All data will be saved on the SHU Research Store with a file name corresponding to the study title e.g. 'Q:\RESEARCH\ATAS'. With the exception of participant personal data, data relating to the trial will be archived for 10 years in line with the Sponsor's requirements. Participant personal data (e.g. phone number, email address and home address) will be archived for 2 years after the end of the study so that participants can be contacted regarding research dissemination. An anonymised description of the available data (metadata), including a list of key variables will be placed on University open-access repository (SHURDA).

The data collected from this project will be suitable for sharing on request because of the broad academic interest in stroke rehabilitation. Other researchers should have the

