opportunity to explore this dataset to develop the field of research without having to repeat the same investigations, and expose patients to unnecessary risk. Original data will be provided on application rather than be offered open access. This is because it may not be possible to ensure that data is completely anonymised. We can only guarantee that data will be pseudo-anonymised. All external users of our data will be bound by a data sharing agreement between the research team and SHU, and the user themselves. Data will be supplied on the condition that their research is non-profit, and that their findings will be published in an open access domain. Data users will not be permitted to share the data with anyone outside of their immediate research team.

SHU storage arrangements conform to GDPR and NHS standards. The Principal Investigator ([name]) will be the custodian of the data and the data processor.

14. Ethical and regulatory considerations

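### Section 7.7 orders all of a participant's data destroyed on request and does not exempt safety or disposition records, which conflicts with the safety recording rules in 12.5 and 12.6

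*Protocol*

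**What the plan says.** Protocol section 7.7 has two tiers. The default is retention: "Any data provided to that point will be used unless the patient requests otherwise". If a withdrawing participant asks for data withdrawal, "all data relating to that participant up until anonymisation of the final dataset will be destroyed". The section carves out no category of record.

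The safety sections are equally unqualified. Section 12.5 states: "All SAEs occurring from the time of start of the intervention until 3 months post cessation of trial intervention will be recorded". The original form goes to the Sponsor, with "a copy to be retained on site". Section 12.6 makes the Principal Investigator responsible for recording related AEs and reporting them to the Sponsor, and for collecting and verifying AEs and SAEs on a database. Neither section excepts participants who withdraw.

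The trial summary lists safety and dropout rate under the primary objective. Section 11 (Table 6) defines safety as the number of related SAEs and AEs, and dropout as "Percentage of individuals that discontinue participation after the study has commenced". Section 6.3 bases the safety progression decision on an absolute count: fewer than 5 related events is Green, 5 to 10 is Amber, and the top band is "Red: >10 adverse events related to the intervention".

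**The concern.** Three kinds of record are needed whatever happens to a participant's outcome data: the safety reports, the allocation, and the fact and timing of withdrawal. Section 7.7 makes no distinction between these and questionnaire scores or blood samples. A site that receives an erasure request therefore has one instruction to destroy everything and another to retain the SAE form, with nothing to say which prevails.

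Two primary feasibility outcomes are exposed. The related-AE count is a go/no-go criterion with no denominator, so a deleted event is not offset by a deleted participant. The dropout rate loses a unit from numerator and denominator together. In both cases the change favours the intervention or the trial. A statistical analysis plan cannot repair this, because it cannot analyse records that the protocol has had destroyed.

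**Working it through.** **Step 1: can the rules be followed together?** Take a participant who has an SAE after the intervention starts, withdraws, and asks for data withdrawal.

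| Rule | What it requires for this participant |
|---|---|
| 7.7 | Destroy all data relating to the participant |
| 12.5 | SAE recorded; original form with the Sponsor; copy kept on site |
| 12.6 | Event collected and verified on the AE/SAE database |

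If the SAE form counts as data relating to the participant, which is the ordinary meaning of the words, the site cannot obey the first row and the other two. For a non-serious related AE, 12.6 requires reporting to the Sponsor and entry on the database, but no section sets a form-retention rule like the one in 12.5.

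**Step 2: baseline figure.** Section 7.3 gives a minimum of 24 participants and 20% attrition: 24 / (1 − 0.20) = 30, the stated target. The plan's own attrition rate corresponds to 0.20 × 30 = 6 dropouts.

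**Step 3: effect on the traffic light.** Let R be the true number of related AEs and e the number belonging to erased participants. The counted number is R − e, which is never above R. With e = 1:
- 5 − 1 = 4: Amber becomes Green.
- 11 − 1 = 10: Red becomes Amber.

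**Step 4: effect on the dropout rate.** With d dropouts among 30, of whom k are erased, the rate moves from d/30 to (d − k)/(30 − k).
- d = 3, k = 1: 3/30 = 10.0% becomes 2/29 = 6.9%.
- d = 6, k = 1, 2, 3: 6/30 = 20.0% becomes 5/29 = 17.2%, 4/28 = 14.3%, 3/27 = 11.1%.

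**Step 5: how much this could shift the traffic light on average.** Assumptions: 15 participants in the exercise arm, all 5 sessions delivered to each (15 × 5 = 75 sessions), at most one AE per session, independent events, all counted as related, and erasure unrelated to having had an event. Each erased exercise participant removes 5 sessions. The number of events is Binomial(n, p), with Red = P(X ≥ 11) and Green = P(X ≤ 4). The rates 12% and 14.7% are the mean and upper figures that section 8.3 gives for earlier studies; 5% is an assumed lower value.

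| AE rate per session | Quantity | 0 erased (n = 75) | 1 erased (n = 70) | 2 erased (n = 65) |
|---|---|---|---|---|
| 5% | P(Green) | 0.679 | 0.728 | 0.775 |
| 12% | P(Red) | 0.286 | 0.214 | 0.151 |
| 12% | P(Green) | 0.045 | 0.066 | 0.097 |
| 14.7% | P(Red) | 0.553 | 0.456 | 0.357 |

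The two section 8.3 rates are driven by treadmill walking, and the protocol expects cycling in bed to be better tolerated. The rows therefore span a range and do not predict this trial's rate.

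**The case against.** The case for leaving the text alone has real force.

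- **Retention is the default.** A loss needs a withdrawal and a separate request for erasure. This stands.
- **Related AEs normally reach the Sponsor first.** Section 12.6 requires related AEs, serious or not, to be reported, and 12.5 sets 24 hours for SAEs. Section 7.7 does not say it reaches back into Sponsor-held reports, and its mention of the final dataset allows a narrower reading limited to research data. This is a fair reading of intent, but the text does not state it. The word *all* is unqualified, and 12.5 also requires a site copy.
- **Dropout has no progression threshold.** Correct: the shift in Step 4 triggers no decision under 6.3. A bare tally of dropouts might also be kept, though no section provides for one.
- **The sizes are constructed.** No request rate is given, and the examples in Step 3 start at a boundary. Section 6.3 also says only that progression will be considered. All of this stands.

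Three stronger inferences are tempting, and the documents do not support them. A reader might infer that 7.7 also contradicts the rule in section 13 that "data relating to the trial will be archived for 10 years". A general retention period can coexist with a specific withdrawal exception, since destroyed data are simply not in the archive. A reader might infer that the erasure window never closes because section 13 says "We can only guarantee that data will be pseudo-anonymised". That sentence explains why original data are shared on application and not openly. It does not say that no anonymisation step will happen. Finally, a reader might infer that people who stop because of an event are the likeliest to ask for erasure, so that the loss is informative. That is possible, but nothing in the protocol bears on it.

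**Conclusion.** The point holds in a limited form. Section 7.7 states a rule, not a gap left to another document. As written, that rule conflicts with sections 12.5 and 12.6 once an erasure request is made. It exposes the related-AE count, which drives a go/no-go decision, and the dropout rate, a primary feasibility outcome, to a loss that can run only in the favourable direction.

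The size is illustrative. A single request can change a traffic-light band only when the true count sits close enough to a boundary. Under the Step 5 assumptions at a 12% event rate, one erased exercise participant lowers the chance of Red from 0.286 to 0.214. These figures assume literal application of 7.7 and at least one request, whose frequency the protocol does not give. The matter is not fatal to the trial, but it should be settled before the first participant consents, because records destroyed under 7.7 cannot be recovered.

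**What to change.** Amend section 7.7 so that, on request, outcome data, interview transcripts and stored samples are removed, while the following are always retained in pseudonymised form:
- AE and SAE reports;
- consent and allocation;
- sessions started;
- date of withdrawal, and the reason if the participant gives one.

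State that these records count in the safety and dropout outcomes, cross-refer to 12.5 and 12.6, and say the same in both versions of the information sheet unless they already do. Naming a fixed cut-off for requests, such as database lock, would be a helpful clarification but is optional.

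The cost is about one paragraph in the protocol and one sentence in each information sheet, submitted as an ethics amendment. The sample size does not change. The downside is that a participant can no longer have this minimal record erased, which is why it must be explained at consent.
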